This is a single-center, prospective cohort study of subjects undergoing clinically indicated PET/CT MPI, with documented coronary artery disease or an intermediate to high pretest likelihood of coronary artery disease. Following the clinical study, the research study is explained to the subjects. Consenting subjects will return on another day (next calendar day or later) for a repeat stress study with Lexercise or a repeat Lexiscan stress PET. Approximately 50 subjects (not more than 16 patients with normal Rubidium-82 or N-13 ammonia PETMPI, 10 healthy volunteers and 24 patients with reversible perfusion defects) will be enrolled in this study. After successful screening and enrollment, 13 random subjects (8 normal and 5 ischemic) will return for repeat Lexiscan PET, and 37 subjects will return for a Lexercise PET/CT MPI. Lexiscan PET will be performed per standard protocol. For Lexercise, a symptom limited exercise treadmill study with Lexiscan injection at peak exercise is performed. Rubidium-82 or N-13 ammonia will be injected and PET/CT images will be obtained in a list mode acquisition. Images will then be unlisted and myocardial blood flow computed.

Number of Subjects Planned

Approximately 50 subjects will be enrolled into the study.

Main Selection Criteria

Subjects will be eligible if they meet all of the following inclusion criteria and none of the exclusion criteria:

Inclusion criteria:

- Age > 18 years
- Clinically indicated Rubidium-82 or N-13 ammonia PET study
- Ten healthy volunteers recruited using web based advertisements.
- Known coronary artery disease (prior percutaneous coronary intervention, prior coronary artery bypass surgery or Q wave MI on ECG) or intermediate to high pretest likelihood of CAD
- Able to exercise on a treadmill
- Able and willing to provide informed consent to participate in the study

Exclusion criteria:

- Contraindications to exercise stress testing such as
 - unstable angina
 - known severe left main coronary artery stenosis
 - severe or uncontrolled heart failure
 - uncontrolled atrial or ventricular arrhythmias
 - symptomatic hypotension or severe hypertension (systolic blood pressure < 90 or > 200 mmHg, respectively)
 - > 1st degree atrioventricular block in the absence of a functioning pacemaker.
- Contraindications to Lexiscan use such
 - Allergy or intolerance to aminophylline or regadenoson

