Combined standard symptom limited exercise stress testing with injection of Lexiscan at peak exercise (Lexercise PET) may be a novel protocol to optimally image maximal endothelium dependent (exercise) and endothelium independent (Lexiscan) alterations in MBF, using relative and absolute myocardial perfusion PET. Symptom limited exercise produces endothelial activation and vasodilation of normal and vasoconstriction of diseased coronary arteries. Addition of vasodilator stress at maximal exercise results in further (maximal) vasodilation of the normal coronary arteries; but minimal or no additional

vasodilation of the vasoconstricted diseased coronary arteries. This may result in improved defect contrast compared to the normal coronary arteries and better detection of CAD. Indeed a prior study demonstrated that defect size is larger with treadmill exercise stress compared to vasodilator stress with dipyridamole.⁸ Also, the precise reasons for larger perfusion defects with exercise compared to dipyridamole PET were not studied; although, true ischemia from exercise was proposed as a possible mechanistic link for larger perfusion defects with exercise. If endothelial dysfunction and true vasoconstriction are imaged with exercise PET, then, we can expect to metabolic abnormalities (switch from fatty acid to glucose metabolism) in the corresponding myocardial segments that may be imaged using tracers of fatty acid metabolism such as β Methyl-*p*-[123I]-iodophenyl-pentadecanoic acid (BMIPP) or C-11 Palmitate. Lastly, quantitative MBF is estimated predominantly with vasodilator stress and occasionally with bicycle exercise stress.⁹ Quantitative PET with Lexercise PET may be a novel method to image combined alterations in MBF related to both endothelium dependent and independent mechanisms of MBF.

II. SPECIFIC AIMS:

The overall purpose of the proposed research study is to examine in detail, using relative and quantitative Rubidium-82 or N-13 ammonia PET, the feasibility, safety, utility and the mechanistic basis of combined symptom limited exercise treadmill test with vasodilator stress compared to vasodilator stress alone in the evaluation of known or suspected coronary artery disease. The following specific aims are proposed:

Aim 1: To **assess the tolerability and safety** of the combined symptom limited exercise and Lexiscan protocol (Lexercise PET) compared to Lexiscan alone (Lexiscan PET).

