Hypothesis 1: Lexiscan will cause further/maximal vasodilation in a subject that is already vasodilated from exercise; therefore, the safety of this protocol needs to be ascertained. Lexiscan is expected to be well tolerated when injected during maximal exercise stress without any increase in major adverse events.

Aim 2: To **assess the image quality** of Lexercise PET compared to Lexiscan.

Hypothesis 2: Image quality as assessed by myocardial count density and heart to liver ratio will be superior with Lexercise compared to Lexiscan. However, misregistration artifacts from upward diaphragmatic creep will be higher with Lexercise compared to Lexiscan.

Aim 3: To compare **relative and absolute PET** with Lexercise compared to Lexiscan PET in identifying CAD.

Hypothesis 3: Lexercise PET offers the advantage of imaging reduced myocardial blood flow from vasoconstriction in diseased territories and maximal vasodilation in normal territories. Therefore, in patients with ischemic scans, the defect contrast on relative will be better with Lexercise compared to Lexiscan PET. We hypothesize that the differences in regional CFR between normal and abnormal territories will be greater with Lexercise compared to Lexiscan.

Significance of the mechanistic questions of this proposal:

The overall goal of this proposal is to evaluate the feasibility, utility and mechanistic underpinnings of a novel protocol incorporating combined maximal symptom limited exercise treadmill test with Lexiscan compared to Lexiscan alone. The combined standard symptom limited exercise stress testing with Lexiscan has several novel clinical and research applications:

1. This protocol provides exercise data (hemodynamic, electrocardiographic and clinical data) combined with high quality PET imaging that is important in patient management.
2. A PET MPI study can be performed with physiological exercise stress using any of the available flow tracers (Rubidium-82, N-13 ammonia, or the new compound BMS747158, an F-18 labeled agent) with minimal radiation exposure to the staff.
3. This protocol makes it feasible to assess both endothelium dependent (exercise) and endothelium independent (Lexiscan) mechanisms affecting MBF.

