Rubidium-82 or N-13 ammonia PET image acquisition:

Following skin preparation and ECG lead placement, patient undergoes a symptom limited standard Bruce exercise treadmill test. At peak exercise (when patient is unable to exercise for more than 1 minute), the treadmill is stopped and patient is immediately positioned on the imaging table. Image acquisition is started with a CT scout image for positioning the heart (10 mA, AP scout, 9 seconds). Then 0.4 mg of regadenoson is given by intravenous push over 10 seconds followed by 10 ml of normal saline flush. Right after the saline flush, 40-60 mCi of Rubidium-82 or 20 mCi of N-13 ammonia is injected and emission imaging started in a list mode fashion started at the time of injection of radiotracer. Following completion of the emission imaging, a CT transmission scan (20 mA, 120 KV, non-gated, free tidal breathing) is obtained for correction of photon attenuation by soft tissues. .

Rest and Lexiscan stress images from the clinical study and the Lexercise stress emission images will be unlisted for analysis into a static file, a gated file and dynamic image frames (36 frames of 5 seconds each, 8 frames of 15 seconds each, and 6 frames of 30 seconds each for stress and 2 groups for rest of 24 frames at 5 seconds each and 8 frames at 30 seconds each). In subjects with serious or bothersome adverse effects, aminophylline will be administered intravenously (1 mg/kg, to a maximum of 150 mg) to alleviate the symptoms.

Myocardial blood flow quantification:

Myocardial blood flow (in ml/gm/min) at rest and after vasodilator stress will be quantified using a software based on GFADS and a 2 compartment model, developed and validated at the Brigham and Women's Hospital.¹³ Rest and peak stress myocardial blood flow will be computed in ml/gm/min and global and regional (vascular territories assigned as described below) coronary flow reserve computed by dividing stress myocardial blood flow by rest myocardial blood flow. Coronary vascular resistance at rest and stress will be computed by dividing mean aortic pressure [derived as 2 (diastolic blood pressure) + systolic blood pressure/3] by myocardial blood flow. In addition to calculating the myocardial blood flow for the left ventricle as a whole, myocardial blood flow will be determined for each of three vascular beds

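### The documents disagree on when Lexiscan is given in the Lexercise protocol: at peak exercise, or after the treadmill has stopped

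*Combined protocol and SAP*

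**What the plan says.** Four places give or imply the timing of the drug.

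- **Synopsis, Design and Methodology:** for Lexercise, "a symptom limited exercise treadmill study with Lexiscan injection at peak exercise is performed".
- **I. Background, section on exercise and vasodilator effects:** the protocol is introduced as "Combined standard symptom limited exercise stress testing with injection of Lexiscan at peak exercise (Lexercise PET". The mechanism that follows has both stimuli acting together: "Addition of vasodilator stress at maximal exercise results in further (maximal) vasodilation of the normal coronary arteries".
- **II. Specific Aims, Hypothesis 1:** "Lexiscan is expected to be well tolerated when injected during maximal exercise stress", with no increase in major adverse events.
- **V. Study Procedures, PET image acquisition:** on reaching peak exercise "the treadmill is stopped and patient is immediately positioned on the imaging table". The next step is "Image acquisition is started with a CT scout image for positioning the heart (10 mA, AP scout, 9 seconds". After that comes the drug: "Then 0.4 mg of regadenoson is given by intravenous push over 10 seconds". A saline flush and the tracer follow.

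The datasheet described under Study Procedures (Before the test) covers doses, hemodynamics, the reason for stopping the test, symptoms and ECG changes. It lists no clock time for treadmill stop or for the injection.

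**The concern.** Three of the four places have the drug given while the patient is at maximal exercise. The fourth, which staff would follow on the day, has it given once exercise has ended and the patient is on the table.

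Timing matters most for safety. Hypothesis 1 is a statement about tolerability at a named moment, and the rationale for Aim 1 says that the safety of combining two full stresses has to be shown before wide clinical use. The site's SPECT experience cited there had not been formally analysed and is reported without injection times, so it does not fill the gap. If the acquisition procedure is followed and the report is worded as in Hypothesis 1, the conclusion will cover a condition in which no subject was studied.

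The second issue is that the interval is neither limited nor recorded. It exists only in the Lexercise scan and has no counterpart in the Lexiscan-alone scan, so comparing a subject's two scans does not remove it. Without the times, nobody can later say how long the gap was or whether it varied between subjects.

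**Working it through.** The plan states no figure for this interval, so there is none to reproduce. The check is a comparison of texts plus one sum.

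**Order of events in the acquisition procedure**

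1. Peak exercise is reached and the treadmill is stopped.
2. The patient is moved to the imaging table. Duration not given; call it T.
3. CT scout, 9 s.
4. Regadenoson push, 10 s.
5. Saline flush, duration not given.
6. Tracer injection, with list-mode acquisition starting at the same time.

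In this sequence peak exercise is the moment that triggers stopping the treadmill. The injection three steps later therefore cannot also be at peak exercise.

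**Time from treadmill stop**

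- Start of push ≥ T + 9 s.
- End of push ≥ T + 9 + 10 = T + 19 s.

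| Transfer time T | Start of push | End of push |
|---|---|---|
| 0 s (lower bound) | 9 s | 19 s |
| 30 s (assumed) | 39 s | 49 s |
| 120 s (assumed) | 129 s | 139 s |
| 180 s (assumed) | 189 s | 199 s |

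Only the first row rests on the documents alone. The other rows show the range under assumed transfer times. All are minimums, because scout set-up is not counted and the flush comes later still.

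**Which hypotheses are touched**

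- *Hypothesis 1* names the timing. Its wording and the procedure conflict directly.
- *Hypothesis 3* names no timing. It says that "Lexercise PET offers the advantage of imaging reduced myocardial blood flow from vasoconstriction in diseased territories", along with maximal vasodilation in normal territories. It depends on timing only through the definition and mechanism in the Background.

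**The case against.** The procedure can be read as the operational detail behind a shorthand. Its sequence opens at peak exercise and asks for immediate positioning, so a short gap is clearly intended. Imaging after exercise is also disclosed elsewhere: the rationale for Aim 2 has the scan starting while the subject is still breathing heavily, and Study Endpoints Assessed places ejection fraction just after stress. The reason given in Hypothesis 1, a subject already vasodilated by exercise, may still hold in early recovery. The Lexercise versus Lexiscan comparison remains valid for the procedure as performed, and no test, sample size or endpoint changes.

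Most of this stands, and it limits the point. It does not remove the contradiction: a short gap after exercise is still not during exercise, and Hypothesis 1 says the latter.

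A reader might go further, in ways the documents do not support:

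- *That the trial tests a different intervention from all its hypotheses.* Only Hypothesis 1 conflicts in terms. The wording of Aims 1 and 3 contains no injection time.
- *That the peak-stress flow and ejection fraction are really recovery values in all 37 Lexercise subjects.* The statistical section uses the term peak stress for Lexiscan-alone scans too, where nobody exercises, so it is not shown to mean peak treadmill effort. The drug is given just before the tracer, and the documents give no rate at which exercise effects fade. The count is also unsettled: 37 in the Synopsis, 34 in Study Methods, and Lexiscan is withheld from subjects with listed abnormalities on the treadmill.
- *That the delay is known to be a minute or more.* Only the 19 s comes from the documents.

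**Conclusion.** The contradiction is real and lies in the current text. As written, the procedure starts the push at least 9 s after exercise ends and completes it at least 19 s after, plus a transfer time that is not stated, limited or recorded. Safety data gathered this way support a conclusion about Lexiscan given shortly after maximal exercise, not during it. This rests on the acquisition procedure being what is actually done; if practice follows the Synopsis instead, it is the procedure text that misdescribes the study.

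For Hypothesis 3 the consequence is indirect. Added variation in flow, ejection fraction or defect size from an uneven delay is plausible, but its size cannot be computed from the documents and none is claimed here. The point should be acted on because it affects what the safety conclusion may say and costs very little to resolve.

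**What to change.** 1. Reconcile the Synopsis, the Background, Hypothesis 1 and the acquisition procedure to one definition of when Lexiscan is given. Which timing is intended is for the investigators to decide.
2. Word Hypothesis 1 and the study conclusions for the timing actually used. The Aims need no change on this account.
3. Add two clock times to the existing datasheet: treadmill stop and regadenoson injection. Tracer time needs no separate entry, since it coincides with list-mode start.
4. Report the stop-to-injection interval descriptively, for example as median and range. State for how many subjects it is missing, since the document is dated September 2016 in an enrolment period that began in 2010.

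The cost is two datasheet entries per Lexercise subject and some rewording, together with a safety conclusion limited to the timing actually used.

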 - Known severe or oxygen dependent bronchoconstrictive or bronchospastic lung disease [e.g., asthma, wheezing, chronic obstructive pulmonary disease (COPD), etc.].
 - Sick sinus syndrome
 - History of heart transplantation.
 - Dialysis
 - Subject requires emergent cardiac medical intervention or catheterization after the clinical study.
 - Documented myocardial infarction (MI) ≤ 30 days prior to enrollment.
 - History of percutaneous coronary intervention (PCI) ≤ 4 weeks prior to enrollment.

- History of coronary artery bypass graft (CABG) \leq 8 weeks prior to enrollment.
- Severe LV dysfunction, with ejection fraction of $< 30\%$
- Serious non-cardiac medical illness (e.g., disseminated malignancy, severe neurological dysfunction at time of baseline PET study) or a social situation which will preclude research study participation
- History of seizure disorder

Discontinuation criteria:

Subjects should be discontinued for the following discontinuation criteria

- Subject does not fulfill inclusion or exclusion criteria
- Subject experiences a serious or intolerable adverse event
- In the Investigator's opinion, the subject is non-compliant with the protocol requirements (protocol violation)
- Subject's health would be jeopardized by continued participation
- Subject wishes to withdraw consent

Lexiscan will not be administered to patients with clinical or EKG evidence on ischemia during exercise treadmill testing. Clinical or EKG abnormalities during treadmill testing that would preclude administration of Lexiscan are listed below:

- a) Clinical
 - a. Severe chest pain
 - b. Severe lightheadedness or dizziness,
 - c. Severe shortness of breath
 - d. Exercise induced hypotension ($> 10\text{mm Hg}$ decrease in systolic blood pressure)
 - e. Exercise induced hypertension (systolic blood pressure $> 210\text{ mm Hg}$)
- b) ECG changes
 - a. Significant ST segment depression ($\geq 2\text{ mm}$)
 - b. Significant ST segment elevation ($\geq 1\text{ mm}$)
 - c. Sustained ventricular or atrial tachycardia,
 - d. Exercise induced heart block

Statistical Plan:

The overall aim of this pilot study of 50 patients is to assess the tolerability, safety, diagnostic accuracy and image quality between Lexiscan with symptom limited exercise compared to Lexiscan alone.

Aim 1. For this aim, we will compare the reported side effect profile for Lexercise to Lexiscan PET, using a Pearson Chi square test. A P-value of <0.05 will be considered significant.

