Risks of withholding medications: Certain medications such as beta-blockers, nitrates, diuretics, calcium channel blockers and bronchodilators may have to be held for 12-24 hours prior to the study. Withholding these medications may result in chest pain or angina, high or uncontrolled blood pressure, high blood glucose, or in very rare instances a heart attack. For these reasons we will only enroll subjects that are clinically stable without uncontrolled angina, hypertension or are acutely ill for any reason. The medications that will be withheld and the length of the time withheld are shown below. To minimize the

risk, the prescribing physician will be consulted to give permission for his patient to withhold the specified medication for the specified length of time.

Hold on the morning of the test

Diabetic agents: Insulin Half of Normal Morning Dose can be taken.

Hold oral Hypoglycemics till after the test completion: Actos, Amaryl, Avandamet, Avandia, Avandaryl, Byetta, Diabeta, Diabinese, Fortamet, Glipizide, Glucophage, Glucovance, Glucotrol, Glyburide, Metformin, Micronase, Prandin

Hold 4-6 hours prior to testing

Nitroglycerine, Deponit, Nitro-Bid, Nitro-Disc, Nitro-Dur, Nitro-Gard, Nitrol, Nitrostat, TransdermNitro, Trasdermal-NTG, Nitro paste

Hold 12 hours prior to testing

Nitro-
Nitrates, Isosorbide Dinitrate Isordil, Dilatrate, Sorbitrate, Isosorbide Mononitrate, Imdur, Ismo, Monoket

Hold 24 hours prior to testing

Bronchodilators Aerolate, Aminophylline, Aquaphyllin, Asmalix, Choledyl, Elizophylline Slo-bib, Slo-Phyllin, Thoe-Dur, Theovent

Calcium Channel Blockers

Amlodipine Cauduet, Lotrel, Norvasc, Diltiazem Cardizem CD, Cardizem SR, Cartia XT, Dilacor XR, Diltia XT, Tiazac, Taztia XT, Felodipine Plendil, Isradipine DynaCirc, Nicardipine, Hydrochloride, Cardene, Cardene SR, Nifedipine Adalat, Adalat CC, Procardia, Procardia XL
Nimodipine Nimotop, Nisoldipine Sular, Verapamil, Hydrochloride, Calan, Calan SR, Covera, Isoptin, Isoptin SR, Verelan

Miscellaneous

Cafergot, Cialis, Levitra, Ranexa, Ranolazine, Trental, Pletal, Viagra.

Hold 48 hours prior to testing

Dipyridamole, Persantine, Aggrenox

Aminophylline: Side effects of aminophylline may include nausea, headache, restlessness, convulsions, rapid breathing, a rapid heart rate, and allergic reactions such as rash.

VIII. POTENTIAL BENEFITS

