No direct benefit is anticipated to individual subjects. The results of this study may benefit society through evaluation of the diagnostic utility of novel protocol utilizing combined symptom limited exercise vasodilator stress test to image endothelium dependent and endothelium independent factors affecting myocardial blood flow.

IX. MONITORING AND QUALITY ASSURANCE

Subject safety will be ensured by strict adherence to inclusion and exclusion criteria and close monitoring. Subjects that experienced serious adverse events during the study will be removed from the study and followed up, but no other study procedures will be performed. We will monitor the subjects closely for seizures and ischemic symptoms. History of seizures is an exclusion criteria for the study. Individuals who experience seizures for the first time during the initial regadenoson study will be excluded from the second regadenoson with exercise study. Intravenous aminophylline, a competitive agonist, will be administered for ischemic symptoms. Subjects with ischemic symptoms will be monitored until complete resolution (current clinical practice). As listed in page 22, study endpoints, safety blood work will be drawn after the Lexiscan and the Lexercise PET study to measure serum troponin T levels. This study does not involve treatment and hence a data safety monitoring board.

This is a pilot clinical study of about 50 subjects. The study PI, [name], will be responsible for monitoring the study procedures after every subject is enrolled, including the accuracy and completeness of the case report form entries, source documents and informed consent after every enrollment. These documents will be appropriately maintained on submission.

Specification of Source Documents

The following information will be included in the source medical records:

- Demographic data (age, sex, and race)
- Inclusion and exclusion criteria details
- Participation in study and signed and dated informed consent forms
- Visit dates
- Medical history and physical examination details
- Key efficacy and safety data
- Adverse events and concomitant medication
- Results of relevant examinations
- Laboratory printouts
- Reason for premature discontinuation

Ethical Conduct of the Study

The investigator(s) and all parties involved in this study will conduct the study in adherence to GCP, ICH Guidelines and the applicable laws and regulations.

Subject Confidentiality

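### The rescue-aminophylline rule has no exception for seizure, although the protocol lists convulsions as a possible aminophylline side effect and states no acute seizure care: a minor, low-cost safety clarification

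*Combined protocol and SAP*

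**What the plan says.** The treatment rule is in section V (Study Procedures), under Rubidium-82 or N-13 ammonia PET image acquisition: "In subjects with serious or bothersome adverse effects, aminophylline will be administered intravenously (1 mg/kg, to a maximum of 150 mg) to alleviate the symptoms". It stands in the part that describes symptom-limited exercise followed by regadenoson, that is, the Lexercise scan.

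Section VII (Risks and Discomfort) says of the same drug: "Side effects of aminophylline may include nausea, headache, restlessness, convulsions, rapid breathing, a rapid heart rate, and allergic reactions such as rash".

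Section IX (Monitoring and Quality Assurance) deals with seizure in two places. On surveillance: "We will monitor the subjects closely for seizures and ischemic symptoms". On continuation: "Individuals who experience seizures for the first time during the initial regadenoson study will be excluded from the second regadenoson with exercise study". It adds that subjects with serious adverse events are "removed from the study and followed up, but no other study procedures will be performed". It also gives a second trigger for the drug: "Intravenous aminophylline, a competitive agonist, will be administered for ischemic symptoms".

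At entry, the exclusion criteria in the Synopsis and in section III bar subjects with "History of seizure disorder" and those with "Allergy or intolerance to aminophylline or regadenoson".

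**The concern.** The section V sentence is an order, not an option, and its trigger is wide. In ordinary reading a seizure is a serious adverse effect, so staff who follow the sentence as written would give a seizing subject a drug for which the protocol itself lists convulsions as a possible effect. A clinician who withheld it would be departing from the written procedure.

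The event is foreseen, since section IX watches for it and legislates for it. The setting also matters. Safety of the combined stress is Aim 1. The rationale for that aim says that safety still has to be established and that the combination has not been used with PET. Section VIII expects no direct benefit to subjects, and ten of them are healthy volunteers who undergo both stress protocols. An emergency that the protocol anticipates should have an instruction that reads the same way to everyone in the room.

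**Working it through.** The plan gives no figure to reproduce. The check is to set every statement on aminophylline beside every statement on seizure or convulsions and ask what each one decides.

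**Statements on aminophylline**

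| Place | What it decides |
|---|---|
| Exclusion criteria (Synopsis, section III) | Allergy or intolerance bars entry. This does not reach a first seizure during a test. |
| Section V, image acquisition | Give for any serious or bothersome effect; no exception. |
| Section VII, Aminophylline | Discloses possible side effects, including convulsions. |
| Section IX | Give for ischemic symptoms; does not say only for these. |

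**Statements on seizure or convulsions**

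| Place | What it decides |
|---|---|
| Exclusion criteria (Synopsis, section III) | A history of seizure disorder bars entry. |
| Section VII, Aminophylline | Convulsions are a possible effect of the rescue drug. |
| Section IX, monitoring | Subjects are watched for seizures. |
| Section IX, first seizure | A first seizure at the initial regadenoson study bars the second study. |

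**General rules that a seizure could trigger.** The discontinuation criteria (Synopsis, section III) cover a serious or intolerable adverse event. Section IX provides removal and follow-up after a serious adverse event.

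**Reasoning**

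1. Does the section V trigger include seizure? Yes, on its words. It covers serious as well as bothersome effects and excepts nothing.
2. Does another statement override it? No. Section IX names one trigger without making it exclusive, so the wider one in section V remains.
3. Do the removal and discontinuation rules settle bedside treatment? No. They govern later participation. If the bar on further study procedures were read to forbid rescue drugs, it would also forbid aminophylline for serious ischemia, which section IX directs.
4. Does any supplied text say what to give or withhold during a seizure? None does. For contrast, the Synopsis and section III itemise the clinical and ECG findings during exercise that preclude Lexiscan. Aminophylline has no comparable withhold rule during the procedure.

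**Dose and exposure.** The dose is 1 mg/kg. Body weights are not given; assuming 60 to 100 kg, it is 1 × 60 = 60 mg to 1 × 100 = 100 mg. The cap acts only above 150 / 1 = 150 kg. Planned enrolment is approximately 50. The number returning for Lexercise is 37 in the Synopsis and 34 in section III. These figures describe what would be given and to how many it could apply; they say nothing about harm. No seizure risk can be computed, because no rate is given and the Lexiscan side-effect list in section VII has no entry for seizure.

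**The case against.** The strongest reply is that a side-effect list is not a list of contraindications. The aminophylline list also contains nausea and headache, which section VII gives as vasodilator effects (6% and 26%) and which the section V sentence is plainly meant to relieve. If listing alone made the drug wrong for an event, the rule would be wrong for those too. This stands. A reader might infer that the protocol orders a contraindicated drug. The documents do not support that: they say nothing on how aminophylline affects a seizure related to regadenoson. What separates seizure from headache is that the protocol singles it out for exclusion, surveillance and a continuation rule, and then leaves its acute treatment to a general symptom-relief sentence.

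Second, sections V and IX can be read together as assigning aminophylline to ischemic symptoms and never to seizure. That reading is reasonable and may be what was intended, but the text does not say it.

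Third, safeguards exist: seizure history is excluded, subjects are watched, and serious events end participation. Lexercise is also the last stress study scheduled, so a bar on a later study is not needed after it. All of this stands and narrows the gap. None of it is bedside treatment, and excluding a history of seizures cannot prevent a first one.

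Fourth, clinicians would probably use judgment. That is likely, and it is a reason to rate the point low.

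Fifth, a flat instruction to withhold aminophylline would itself be a clinical decision without support in the documents, and would leave unclear what to do for a subject with both seizure and ischemia. This is right, and the remedy has to leave room for the physician.

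**Conclusion.** The concern holds as a minor safety correction. A mandatory rule, read literally, covers an anticipated event for which the protocol gives no acute care, using a drug whose listed side effects include convulsions, and nothing in the supplied text overrides it.

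Its size is unknown. There is no seizure rate and no information on the direction or degree of any effect of aminophylline in this setting. No endpoint, sample size or analysis depends on it.

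The conclusion assumes that a seizure counts as a serious adverse effect and that the section V sentence is followed as written. It is also confined to the supplied text: consent pages were removed, and a laboratory emergency procedure outside the protocol may cover seizure. It would therefore be wrong to conclude that the site has no seizure plan, or that subjects are unprotected.

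**What to change.** - **Section V, image acquisition.** After the trigger, insert: other than seizure. Then add a sentence along these lines: a seizure is managed by standard acute care; aminophylline is not given routinely and is used only on the responsible physician's judgment, for example for concurrent ischemia under section IX.
- **Section IX.** Keep the ischemic-symptom trigger as it is and add a cross-reference to the amended section V sentence, so that a subject with both seizure and ischemia is covered.
- **Confirmation.** The investigator should confirm the clinical wording, since the documents do not settle how aminophylline acts in a seizure.

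The cost is one clause, one sentence and a cross-reference. Visits, data collection, sample size and analysis stay the same. Because the physician's discretion is written in, the change does not replace one rigid order with another.
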